11.2.3 Documentation

All AEs that occur within the period of observation for the study must be documented in the eCRF with the following information, where appropriate. (The period of observation for the study is described in Section 11.2.)

- AE name or term
- When the AE first occurred (start date and time)
- When the AE stopped (stop date and time or an indication of "ongoing")
- Severity of the AE
- Seriousness (hospitalization, death, etc.)
- Actions taken
- Outcome
- Investigator opinion regarding the AE relationship to the IP

11.2.4 Treatment of Adverse Events

Adverse events that occur during the study will be treated, if necessary, by established standards of care. If such treatment constitutes a deviation from the protocol, the participant may continue

in the study. The decision about whether the participant may continue in the study will be made by the sponsor after consultation with the investigator and/or medical monitor.

If AEs occur in a participant that are not tolerable, the investigator must decide whether to stop the participant's involvement in the study and/or treat the participant. Special procedures may be recommended for the specific IP, such as the collection of a blood sample for determining plasma concentrations of IP, specific tapering procedures, or treatment regimens, as appropriate.

For double-blinded studies, it is not necessary to unblind a participant's treatment assignment in most circumstances, even if an SAE has occurred. If unblinding is necessary, see Section 9.6 for a description of the unblinding procedures.

11.2.5 Follow-up

Any AE will be followed (up to a maximum of 30 days after the last dose of IP) to a satisfactory resolution, until it becomes stable, or until it can be explained by another known cause(s) (i.e., concurrent condition or medication) and clinical judgment indicates that further evaluation is not warranted. All findings relevant to the final outcome of an AE must be reported in the participant's medical record and recorded on the eCRF page.

11.2.6 Reporting

11.2.6.1 Serious Adverse Events

In the event of any SAE reported or observed during the study, whether or not attributable to the study drug, site personnel will report the event to ICON (ICON plc Pharmacovigilance) by email within 24 hours of notification of event in accordance with procedures described in the Study Reference Manual and/or SAE Study Specific Procedure. Site personnel will follow up with a written report to the sponsor on the next working day.

SAE Report Forms will be provided to the clinical research unit to assist in collecting, organizing, and reporting SAEs and follow-up information.

All SAEs should be followed to their resolution, with documentation provided to the sponsor, medical monitor, and ICON on a follow-up SAE Report Form.

At the time of first notification, the investigator or designee should provide the following information, if available:

- Protocol number
- Reporter (study site and investigator)
- Suspect IP
- Participant's study number
- Participant's year of birth
- Participant's gender
- Date of first dose of IP
- Date of last dose of IP, if applicable

- Adverse event term
- Date of occurrence of the event
- A brief description of the event, outcome to date, and any actions taken
- The seriousness criteria(on) that were met
- Concomitant medication at onset of the event
- Relevant medical history information
- Relevant laboratory test findings
- Investigator's opinion of the relationship to IP ("Is there a reasonable possibility that the IP caused the SAE? Yes or No?")
- Whether and when the investigator was unblinded as to the participant's treatment assignment

Any missing or additional relevant follow-up information concerning the SAE should be sent to ICON (ICON plc Pharmacovigilance) as soon as possible with the following minimal information (initial report, adverse event, date of occurrence, participant identification, study number, IP, and site number); this will allow the follow-up information to be linked to the initial SAE report.

Specific information may be requested by ICON plc Pharmacovigilance using a follow-up request form or via email communication.

The investigator is required to comply with applicable regulations (including local laws and guidance) regarding the notification of his or her health authorities, Human Research Ethics Committee (HREC), principal and coordinating investigators, study investigators, and institutions. Each investigator is obligated to learn about the reporting requirements for investigators in his/her country. The study monitor may be able to assist with this.

11.2.6.2 Adverse Drug Reactions

All ADRs should be reported by the investigator in the eCRF.

Suspected serious ADRs must be reported to the sponsor immediately, regardless of the time elapsed since the end of the observation period.

11.2.6.3 Nonserious Adverse Events

Nonserious AEs will be recorded in the eCRF and reported in accordance with the safety management plan.

11.3. Special Considerations

11.3.1 Pregnancy

Not applicable – participants are postmenopausal women. Women of childbearing potential are not eligible for participation.

12. DATA SAFETY MONITORING BOARD

A data safety monitoring board will not be used in this study.

13. STATISTICS

13.1. Statistical Analysis

This section presents a summary of the planned statistical analyses. An SAP that describes the details of the analyses to be conducted will be written prior to database lock.

An analysis of covariance (ANCOVA) model will be used to assess treatment differences in change from baseline for vaginal pH, vaginal cytology, dyspareunia, and most bothersome symptom, using baseline score as a covariate. With no formal testing planned for this study, the *P* values will be informational.

Summary statistics will be provided for the variables described below. For continuous variables, these statistics will typically include the number of participants, mean, standard deviation (SD), median, minimum, and maximum. For categorical variables, these statistics will typically include the number and percentage of participants in each category. The denominator for percentage will be based on the number of participants appropriate for the purpose of analysis.

For all calculations of change from baseline, the last observation recorded before the first administration of the insert (DARE-VVA1 or placebo) will be considered as the baseline observation.

13.1.1 Analysis Populations

The following 3 analysis populations are planned for this study:

- Safety: all participants who are enrolled and receive any amount of planned IP. This population is used for safety analyses.
- Intent-to-treat (ITT): all randomized participants. This population will be used for the analysis of secondary efficacy endpoints.
- PK: all participants who receive at least 1 dose of IP and provide at least 1 quantifiable PK plasma sample. This population will be used for analyses of PK parameters.

All analyses will be performed on non-hysterectomized participants, hysterectomized participants, and all participants taken together. If a participant is randomized incorrectly or is administered the incorrect IP, analyses of the ITT population will be based on the assigned treatment whereas all other analyses will be based on the actual treatment.

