STATISTICAL METHODS	
General:
 
For the purpose of all safety, efficacy, and other analyses where applicable, baseline is defined as the last measurement before the start of study drug administration.
 
Continuous endpoints will be summarized with number (n), mean, standard deviation, median, minimum, and maximum. In addition, change from baseline values will be calculated at each time point and summarized descriptively. For categorical endpoints, descriptive summaries will include counts and percentages.
 
Analysis Populations:
 
The ITT population, defined as all randomized participants, will be used to summarize participant disposition, demographics and baseline characteristic summaries, efficacy endpoints, and exploratory endpoints.
 
Efficacy evaluations include changes in vaginal pH, changes in vaginal cytology (maturation index; percentage of basal and superficial cells), change in dyspareunia, and change in most bothersome symptom. These will be summarized using the ITT population. For the analysis the exploratory endpoints, results from the MENQOL questionnaire and the Usability and Acceptability questionnaire will be summarized over time from baseline in the ITT population.
 
An analysis of covariance (ANCOVA) model will be used to assess treatment differences in change from baseline for vaginal pH, vaginal cytology, and most bothersome symptom, using baseline score as a covariate. With no formal testing planned for this study, the P values will be informational.
 
The Safety population, defined all participants who are enrolled and receive any amount of planned IP, will summarize the recorded AEs, clinical laboratory safety tests, vital signs, ECG results, physical examination findings, and any other parameter relevant for safety assessment.

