13.1.6 Pharmacodynamics and Efficacy Analysis

Efficacy variables will be summarized and analyzed using the ITT population, unless otherwise specified.

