13.1.6.2 Secondary Analyses

The secondary efficacy endpoints are the following:

- Change of vaginal pH from baseline to Day 57
- Change in vaginal cytology (maturation index; percentage of basal and superficial cells) from baseline to Day 57
- Change in most bothersome symptom from baseline to Day 56
- Change in severity of dyspareunia from baseline to Day 56
- Correlation between exposure and local changes

Descriptive summaries (mean, SD, median, minimum, and maximum) involving change of vaginal pH and vaginal cytology will be presented by treatment group at each time point. In addition, an ANCOVA model will be used to assess treatment differences in change from baseline for vaginal pH, vaginal cytology, dyspareunia, and most bothersome symptom, using baseline score as a covariate. The *P* values will be informational, and no formal testing is planned for this study.

The change in severity from baseline for the most bothersome symptom identified by participants at screening will be summarized categorically by treatment group (see Section 10.3.3.3 for assessment details). In addition, the change in severity from baseline will also be summarized descriptively for each of the 5 symptoms evaluated at each time point.

For assessments of dyspareunia, change in severity from baseline will be summarized descriptively by time point and by treatment group. A categorical summary of severity will be presented by treatment group at each time point.

Pharmacodynamics will be assessed by correlating the dose administered to exposure of tamoxifen in plasma, and then by relating the exposure to local vaginal change in cytology and pH as well as to the reported symptomatology over 56 days. Additional details of this analysis will be provided in the SAP.

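### Does placing the exposure-response correlation in ITT conflict with a PK population that placebo women are not expected to enter?

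*Combined protocol and SAP*

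**What the plan says.** Section 13.1.6.2 includes "Correlation between exposure and local changes" among the secondary efficacy endpoints. Section 13.1.1 defines ITT as all randomized participants and says "This population will be used for the analysis of secondary efficacy endpoints". Section 13.1.6 repeats the default: "Efficacy variables will be summarized and analyzed using the ITT population, unless otherwise specified".

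Section 13.1.1 defines the PK population as "all participants who receive at least 1 dose of IP and provide at least 1 quantifiable PK plasma sample" and adds "This population will be used for analyses of PK parameters". For a participant randomized or dosed in error, "analyses of the ITT population will be based on the assigned treatment whereas all other analyses will be based on the actual treatment".

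The method in Section 13.1.6.2 has two steps. The first is "correlating the dose administered to exposure of tamoxifen in plasma"; the second relates exposure to cytology, pH and symptoms. No exposure metric, type of correlation or rule for placebo values is given. The same section leaves further detail of this analysis to the SAP, which Section 13.1 says will be written before database lock.

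**The concern.** One endpoint appears to sit under two sets of rules. Its response side falls in ITT by assigned treatment; its exposure side comes from PK parameters, analyzed in the PK population by actual treatment. SERMs are barred before and during the study (Sections 8.2.2 and 9.7.2), so a correctly dosed placebo woman should have no quantifiable tamoxifen or metabolite. That leaves 8 of 40 ITT women outside the population that supplies exposure. The reference to administered dose sounds like the actual-treatment rule, and the Synopsis list of ITT efficacy evaluations, which ends "change in dyspareunia, and change in most bothersome symptom. These will be summarized using the ITT population", does not include this endpoint.

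The stake is dose selection. Section 7.3 includes the lower doses partly to look for a maximally effective dose below 20 mg. If response is flat across active doses, adding placebo at zero exposure still produces a correlation, and all of it is the placebo-active difference. A reader could take it as evidence that more exposure gives more effect.

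**Working it through.** **Counts.** Five groups of 8 give 5 × 8 = 40 women, as Section 13.2 states. Without placebo there are 4 × 8 = 32. Within a hysterectomy stratum (4 per arm) the numbers are 20 and 16.

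**Do the passages conflict?**

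- *Source of exposure values.* Section 13.1.1 says which population is used to analyze PK parameters. It does not say that exposure values used elsewhere may come only from that population. The Synopsis (Study Design) and Section 7.1 provide serial PK sampling in every treatment group, and the Synopsis names matching placebo in the Day 1 PK schedule. Placebo women therefore have PK results, presumably below quantification. ITT can be applied with 40 women; what is missing is how those results enter.
- *Assigned or actual treatment.* That rule operates only after a randomization or dosing error, and Section 9.3 allows no dose adjustment. Otherwise assigned and administered dose are the same.
- *Synopsis omission.* The Synopsis describes the exposure-response analysis in its pharmacodynamics paragraph. Its absence from the ITT list does not assign it to another population.

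**How far can the two versions differ?** Inputs:

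- Exposure = dose × 5.8/13 = 0.446 ng/mL per mg (pilot median at 13 mg, Section 5.3), with log-normal variation, CV 60% or 100% (assumed); placebo = 0. The scale factor does not affect the correlations.
- Full effect: pH change of -2.0 (pilot median paired difference, Section 5.3). Placebo change 0, -0.5 or -1.0 (assumed).
- SD of pH change: the pilot range of 1.5 to 2.5 in four women gives 1.0/2.059 = 0.49, so 0.5, 0.75 and 1.0 were used.
- Spearman correlation of exposure with pH change. Negative values mean more exposure goes with a larger fall in pH.

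The percentages below are of the placebo-to-maximal difference at 1/5/10/20 mg. The flat, graded and no-effect rows use 2,000 simulated trials per scenario. The later-plateau rows use 1,500, at CV 60% and placebo change/SD of 0/0.5, 0/1, -0.5/0.75 and -1/1.

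| True response | 32 active: mean rho | 32 active: P<0.05 | 40 with placebo at 0: mean rho | 40: P<0.05 |
|---|---|---|---|---|
| Flat from 1 mg (100% at every dose) | -0.01 to 0.01 | 4-6% | -0.25 to -0.48 | 33-96% |
| Plateau from 5 mg (1 mg at 25% or 50%) | -0.15 to -0.53 | 14-97% | not needed here | not needed here |
| Plateau from 10 mg (25/60/100/100%) | -0.25 to -0.67 | 29-100% | not needed here | not needed here |
| Graded (25/60/80/100%) | -0.21 to -0.66 | 22-100% | -0.30 to -0.79 | 51-100% |
| No effect | about 0 | 4-5% | about 0 | 4-5% |

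With Pearson on raw exposure, the flat case in 40 women weakens to r of -0.12 to -0.34, with P<0.05 in 11-64%.

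**Reading the table.** The gap between versions is starkest in the first row, where 1 mg is already maximal. Section 7.3 speaks only of a maximum below 20 mg, which could equally be 5 or 10 mg. In those cases the active-only correlation is also clearly non-zero. On the same four settings the graded curve gives -0.23 to -0.66, almost the same as the 10 mg plateau. Neither version separates a plateau from a gradient.

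**The case for a change.** The strongest case for a change is the first row. In a design that looks for a plateau, one reading gives a nominally significant correlation in 33-96% of trials and the other in 4-6%. An independent simulation (SD 0.5 to 1.5, CV 30-80%, effect 2.0) agrees: Spearman 0.31 to 0.48 in size with placebo pooled, against about zero without. The direction depends on none of the assumed values. Section 13.2 says the study is meant to guide later ones, so informational P values do not make a misread correlation harmless. Two or three sentences would settle the matter.

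Part of this stands. A pooled correlation includes the placebo-active difference and should be labeled so, and the protocol does not say how placebo or below-quantification exposure is handled. The inference that the population must be changed does not stand. Both analyses are legitimate. Pooling placebo at zero is more sensitive to a graded response (P<0.05 in 51-100% of trials against 22-100%), and with no effect at any dose both versions stay at 4-5%. The active-only version protects the reader only if 1 mg is already maximal. Whether active arms differ is answered by the treatment comparisons and summaries by group that Section 13.1.6.2 already requires.

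**Conclusion.** No change to the plan is needed. The passages leave a gap rather than give incompatible instructions: the endpoint is in ITT, placebo women have PK results, and the handling of those results is among the details left to an SAP due before database lock. A sensible SAP author will name the exposure metric and the rule for placebo and below-quantification values. That author can show the correlation with and without placebo, noting that the pooled version includes the placebo-active difference.

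Choosing between 40 and 32 women is a trade-off. It matters most if response is flat from 1 mg (mean Spearman -0.25 to -0.48 against about zero). For plateaus starting at 5 or 10 mg, and for a graded response, the active-only correlation is also non-zero. The endpoint is secondary, the study is unpowered, P values are informational, and following the text as written produces no wrong result.

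The sizes depend on an assumed placebo change and exposure CV, on dose-proportional exposure, and on a pH effect and SD from four women in an uncontrolled pilot. That placebo women have no quantifiable drug is an inference from the SERM exclusions; the protocol does not state it. The SAP's text on this analysis is not in the documents supplied, so whether it already settles the rule cannot be seen.

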13.1.2 Study Participants and Demographics

13.1.2.1 Disposition and Withdrawals

The numbers of participants randomized, completing, and withdrawing, along with reasons for withdrawal, and the number of participants in each analysis population will be tabulated by treatment group and overall.

13.1.2.2 Protocol Deviations

A protocol deviation is defined as any intentional or unintentional change to, or noncompliance with, the approved protocol procedures or requirements. Deviations may result from the action or

inaction of the participant, investigator, or site staff. Examples of deviations include, but are not limited to:

- Failure to adhere to study exclusion and inclusion criteria
- Failure to comply with dispensing or dosing requirements
- Use of medications, food, drink, herbal remedies, or supplements that are specifically prohibited in the protocol
- Missed or out-of-window visits
- Drug dosing not administered within the time frame specified in the protocol
- Failure to adhere to test requirements, including vital signs, laboratory tests, physical examinations, PK blood draws, medical history, etc. – either tests not done, incorrect tests done, or not done within the time frame specified in the protocol
- Procedural deviations such as incorrect storage of IP, failure to update the ICF when new risks become known, failure to obtain HREC approvals for the protocol and ICF revisions

At the outset of the study, a process for defining and handling protocol deviations will be established. This will include determining which violations will be designated “key,” requiring immediate notification to the medical monitor and Daré Bioscience Australia Pty LTD. The investigator is responsible for seeing that any known protocol deviations are recorded and handled as agreed.

The number of participants with key/non-key protocol deviations and/or eligibility deviations will be tabulated in categories by treatment group and overall.

13.1.2.3 Demographics and Other Baseline Characteristics

These analyses will be conducted for the Safety and ITT populations.

Demographic variables will include age, height, weight and BMI. Information on race and ethnicity will be collected for any eventual analysis of differences in response to the IP, in accordance with local regulatory requirements. These will be summarized descriptively.

Baseline participant characteristics will include medical history, vaginal speculum examinations, mammograms and CSTs. These will be summarized by treatment group and overall.

13.1.3 Exposure and Compliance

Investigational product administration will be summarized in terms of each participant’s total dose, total number of missed doses, duration of exposure, and overall percentage compliance for the IP. Descriptive statistics for these quantities, including the mean, median, SD, minimum, maximum, and quartiles, will be provided by treatment group.

13.1.4 Safety and Tolerability Analyses

Safety analyses will be conducted using data from the safety population (as defined in Section 13.1.1). Descriptive statistics will be calculated for safety data and presented by visit and treatment group for quantitative safety data, and frequency counts will be compiled for classification of qualitative safety data. Safety variables include treatment-emergent adverse

events (TEAEs), clinical laboratory values, vital signs, ECG readings, physical examination results, endometrial thickening in women who have not undergone hysterectomy, and prior and concomitant medications. No formal inferential analyses will be conducted for safety variables, unless otherwise noted.

13.1.4.1 Adverse Events

All AEs will be coded using the Medical Dictionary for Regulatory Activities (MedDRA), Version 24.0 or higher.

An AE is defined as treatment emergent if the first onset or worsening is after the first administration of IP (DARE-VVA1) and not more than 30 days after the last administration of IP.

The number and percentage of participants with TEAEs will be displayed for each treatment group by system organ class and preferred term. Summaries of TEAEs by severity and relationship to IP will also be provided. All TEAEs leading to IP discontinuation and/or study discontinuation will be summarized separately.

Serious adverse events will be summarized separately in a similar manner by treatment group. Summaries of SAEs by severity and relationship to IP will also be provided. Participant listings of AEs, SAEs, and AEs causing discontinuation of IP will be produced.

